### 4.6 Dose Proportionality

Dose proportionality of the 400mg and 800mg ALXN1210 doses may be assessed for the following PK parameters:

- dose-normalized AUCt
- dose-normalized Cmax (Cohort 1, 2 and Cohort 3 after first dose)

The parameters will be analyzed using the power model [1], where the ratio of geometric means and the corresponding 90% confidence interval will be derived. Dose proportionality will be concluded if the 90% confidence interval of the ratio contains 1.

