5.1.1. Clinical Studies

ALXN1210 has been administered safely to healthy subjects in single intravenous (IV) doses of 200 mg and 400 mg in a single ascending dose (SAD) study (Study ALXN1210-HV-101, N = 14) and in multiple IV doses of 400 mg and 800 mg on an every 4 week (Q4W) regimen in an ongoing multiple ascending dose (MAD) study (Study ALXN1210-HV-102, N = 16). The starting doses of ALXN1210 in these two studies were selected to assess safety in healthy volunteers but also to have measurable pharmacologic activity (eg, inhibition of complement activation) based on the therapeutic exposure required with eculizumab. No safety concerns have been identified in either of the Phase 1 studies, both of which were randomized, blinded, and placebo controlled. In the completed Study ALXN1210-HV-101 (SAD), no serious adverse drug reactions, treatment discontinuations, or deaths were reported.

Conclusions from Study ALXN1210-HV-101 are as follows:

- ALXN1210 exhibited prolonged PK exposure with mean geometric half-life estimates of 32.4 days and 30.8 days following single doses of 200 and 400 mg, respectively.
- The PK parameters (AUC_t , AUC_∞ , and C_{max}) increased in a slightly less than dose proportional manner over the studied range of 200 to 400 mg based on the protocolspecified statistical analysis.
- Following single IV infusion (200- and 400-mg) dose administrations of ALXN1210, all 6 PD variables showed dose-dependent reductions from Baseline. The effect of ALXN1210 on these PD variables was immediately evident after EOI. At the EOI,

the mean free C5 serum concentrations and cRBC hemolysis activity were inhibited by > 99% and > 97%, respectively.

- The duration of the effect was longer following a 400-mg dose than a 200-mg dose.
- All subjects were negative for ADA through Day 150.

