8.3. Dose Rationale

The geometric mean (CV%) ALXN1210 half-life in Study ALXN1210-HV-101 ranged from 30.8 (10.2%) to 32.4 (16.2%) days over the studied doses. Following single IV infusion (200-and 400-mg) dose administrations of ALXN1210 to healthy volunteers, all studied PD variables showed dose-dependent changes from baseline that recovered back to baseline. The effect of ALXN1210 on these PD variables was immediately evident after EOI. At the EOI, the mean free C5 serum concentrations and cRBC hemolysis activity were inhibited by > 99% and > 97%, respectively. In ongoing Study ALXN1210-HV-102, ALXN1210 IV doses of 400 every 4 weeks and 800 mg every 4 weeks are being studied to assess PK, PD, and tolerability in healthy volunteers. The PK, PD, and tolerability data from the non-Japanese studies (Study ALXN1210-HV-101 and Study ALXN1210-HV-102) will be compared with the data from the current study to assess PK, PD, and tolerability bridging between Japanese and non-Japanese healthy volunteers. In the current study, dose escalation (400 mg to 800 mg single dose) and dose progression (800 mg single dose to 800 mg multiple dose) will be decided upon SRC review of the safety and tolerability data from the preceding cohort.

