#### Pharmacokinetic Endpoints

The following PK parameters will be evaluated:

- Observed maximum serum concentration following all ALXN1210 doses (Cmax) following single dose (Cohort 1 and 2) and doses 1 and 5 (Cohort 3);
- Dose-normalized  $C_{max}$ , following single dose (Cohort 1 and 2) and doses 1 and 5 (Cohort 3);
- Time to maximum observed serum concentration (tmax) following single dose (Cohort 1 and 2) and doses 1 and 5 (Cohort 3);
- Trough serum concentrations (Ctrough) just prior to Doses 2 to 5, and 28 days after the 5th dose (Cohort 3);
- Area under the serum concentration versus time curve from time 0 to the last quantifiable concentration (AUCt) after single dose (Cohort 1 and 2) and after dose 5 (Cohort 3);
- Dose-normalized AUCt after single dose (Cohort 1 and 2) and following dose 5 (Cohort 3);
- AUC from time 0 (dosing) to the end of the dosing interval (AUC $\tau$ ) following doses 1 and 5 (Cohort 3). Following Dose 5, calculated over dosing interval (28 days);
- Terminal-phase elimination rate constant ( $\lambda_z$ ) after single dose (Cohort 1 and 2) and after dose 5 (Cohort 3);
- Terminal elimination half-life (t/2) after single dose (Cohort 1 and 2) and after dose 5 (Cohort 3);
- Total body clearance of drug from the serum (CL) after single dose (Cohort 1 and 2) and after dose 5 (Cohort 3);
- Volume of distribution at steady state (Vss) (Cohort 3);
- Assessment of steady state (Cohort 3);
- Accumulation at steady state (R) after the fifth dose (Cohort 3).

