#### 4.2. Sample Size and Power

The sample size of 4 subjects in each of the single-dose cohorts (Cohorts 1 and 2) and 6 to 8 subjects in the 800 mg multiple-dose cohort will allow for the characterization of the central tendency of PK parameters as they relate to ALXN1210 and to gain initial knowledge of PK/PD relationships in Japanese subjects. To ensure future modeling and simulations are accurate, it is preferred to estimate the PK parameters with a maximum imprecision of < 25% following the IV administration of ALXN1210. Six subjects in Cohort 3 will provide 23.3%

maximum imprecision (Table 1) for the estimation of area under the serum concentration versus time curve from time 0 extrapolated to infinity (AUC $\infty$ ), in terms of the relative distance of the lower 90% confidence limit from the observed PK parameter that will be obtained with 80% assurance and assuming the within-subject SD of the log-transformed AUC $\infty$  is as much as 0.19.

Table 1:	Estimation of the Maximum Imprecision in the Estimate of PK	
	Parameters for Selected Sample Sizes	

Number of Subjects on Active	Maximum Imprecision (%)
4	33.6
6	23.3
8	18.9

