- Time to maximum observed serum concentration (tmax) following single dose (Cohort 1 and 2) and doses 1 and 5 (Cohort 3);
- Trough serum concentrations (Ctrough) just prior to Doses 2 to 5, and 28 days after the 5th dose (Cohort 3);
- Area under the serum concentration versus time curve from time 0 to the last quantifiable concentration (AUCt) after single dose (Cohort 1 and 2) and after dose 5 (Cohort 3);
- Dose-normalized AUCt after single dose (Cohort 1 and 2) and following dose 5 (Cohort 3);
- AUC from time 0 (dosing) to the end of the dosing interval (AUCτ) following doses 1 and 5 (Cohort 3). Following Dose 5, calculated over dosing interval (28 days);
- Terminal-phase elimination rate constant ( $\lambda_z$ ) after single dose (Cohort 1 and 2) and after dose 5 (Cohort 3);
- Terminal elimination half-life (t/2) after single dose (Cohort 1 and 2) and after dose 5 (Cohort 3);
- Total body clearance of drug from the serum (CL) after single dose (Cohort 1 and 2) and after dose 5 (Cohort 3);
- Volume of distribution at steady state (Vss) (Cohort 3);
- Assessment of steady state (Cohort 3);
- Accumulation at steady state (R) after the fifth dose (Cohort 3).

All pharmacokinetic parameters will be listed for each individual subject and summarized by treatment group using the following descriptive statistics.

- N (the number of subjects)
- Arithmetic mean
- SD
- CV
- Geometric mean
- Geometric CV

C15045 (ALXN1210-HV\_104) SAP Final 2.0 - 09Oct2016.doc

Page 10 of 13

- Median
- Minimum
- Maximum

Some PK parameters may not be calculated for all or some subjects if the concentration data are not deemed to be amenable to evaluation. Explanations for PK parameters that could not be estimated may be provided in the Clinical Study Report (CSR).

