## 5. CONVENTIONS

All listings will be ordered by treatment and subject number and will include all enrolled subjects. All data will be presented by the dose level of treatment.

For all tables, except PK parameter tables, descriptive statistics for min, max will be presented with the same number of decimal digits as the original values, and with one more decimal digit than the original data for mean and median; standard deviation will be reported with 2 or more decimal digits than the original.

For PK, the individual and summaries of PK parameter results will be reported in 3 significant digits in the listings and in the tables with the following exceptions:

- Tmax will be presented as follows: individual minimum, and maximum values will be reported exactly as the raw data are reported
- % CV will be presented to 1 decimal place

Page layout of tables and listings in landscape mode will be produced in Microsoft Word. Details of page layout will be provided in the tables figures and listings (TFL) shell document.

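### Could Cohort 3 exposure after dose 5 enter the AUCt dose-proportionality test and make a proportional drug look supra-proportional?

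*SAP*

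**What the plan says.** SAP 4.6 is permissive: "Dose proportionality of the 400mg and 800mg ALXN1210 doses may be assessed for the following PK parameters". Two parameters follow. Dose-normalised Cmax carries a qualifier, "Cohort 1, 2 and Cohort 3 after first dose"; dose-normalised AUCt carries none. Both go into a power model, and proportionality is concluded if the 90% confidence interval for the ratio of geometric means contains 1.

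The endpoint list in SAP 2.2, repeated in SAP 4.5, shows where the AUC parameter exists: "Dose-normalized AUCt after single dose (Cohort 1 and 2) and following dose 5 (Cohort 3"). After dose 1, Cohort 3 has AUC over the dosing interval but no AUCt. Dose-normalised Cmax, by contrast, is derived in Cohort 3 after both dose 1 and dose 5.

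Three other places bear on how the data are grouped. The opening of SAP 4 equates treatment group with the dose cohorts, and SAP 4.5 summarises PK parameters by treatment group. Protocol 19.4 summarises by cohort. SAP 5 says "All data will be presented by the dose level of treatment".

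**The concern.** The contrast in SAP 4.6 is worded by dose, and Cohorts 2 and 3 both receive 800 mg. Someone programming from the AUCt line alone, with the SAP 5 convention in mind, could put every 800 mg value of the listed parameter into one group. Cohort 3 would then contribute AUCt after dose 5.

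Cohort 3 is dosed every 28 days, and the half-life in the earlier study "ranged from 30.8 (10.2%) to 32.4 (16.2%) days over the studied doses". More than half of each dose is still in the body when the next is given, so AUCt after dose 5 is about twice the single-dose value. The test would then report accumulation as supra-proportionality.

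The earlier non-Japanese study found that exposure "increased in a slightly less than dose proportional manner over the studied range of 200 to 400 mg". Protocol 8.3 plans a bridging comparison with non-Japanese data, so a false signal in the opposite direction might be taken for an ethnic difference.

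**Working it through.** The SAP gives no figure to reproduce here, so the check sizes each reading of the AUCt line.

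**Inputs**
- Half-life T: 30.8 and 32.4 days (Protocol 8.3).
- Follow-up: 119 days (Cohort 1), 139 days (Cohort 2), 185 days after dose 5 (Cohort 3); five doses 28 days apart (Protocol synopsis, duration of treatment).
- Subjects: 4, 4, and 6 to 8 (Protocol 8.1).
- SD of log AUC: 0.19 (SAP 4.2). The SAP uses it "assuming the within-subject SD of the log-transformed AUC"; treating it as a between-subject SD is an assumption, so 0.15 and 0.30 are shown too.
- Further assumptions: exactly proportional kinetics, mono-exponential decline, and concentrations quantifiable to the last visit.

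**Step 1, rates.** k = ln 2 / T = 0.0225 / 0.0214 per day. The fraction left after 28 days is r = exp(-28k) = 0.533 / 0.549.

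**Step 2, single-dose AUCt as a fraction of AUC to infinity.**
- Cohort 1: 1 - exp(-119k) = 0.931 / 0.922.
- Cohort 2: 1 - exp(-139k) = 0.956 / 0.949.
- Ratio, Cohort 2 to Cohort 1: 1.027 / 1.030. The 3% comes only from the later last visit in Cohort 2.

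**Step 3, Cohort 3 after dose 5.** The carry-over factor is 1 + r + r² + r³ + r⁴ = 2.048 / 2.108. Multiplying by 1 - exp(-185k) gives 2.016 / 2.068. Relative to Cohort 1 this is 2.164 / 2.244.

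**Step 4, pooled 800 mg group.** The geometric mean ratio to Cohort 1 is exp{[4 ln(C2/C1) + n₃ ln(C3/C1)] / (4 + n₃)}.
- n₃ = 6, T = 30.8: exp{[4 ln 1.027 + 6 ln 2.164] / 10} = 1.61; with T = 32.4, 1.64.
- n₃ = 8: 1.69 / 1.73.

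**Step 5, the decision rule.** With two dose levels the power model reduces to a two-group comparison on the log scale. Simulation used a pooled-variance 90% interval and 100,000 runs for all entries except the first row at SD 0.15 and 0.30, which used 40,000. Entries show how often the interval wrongly excludes 1.

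| Data used for AUCt | Expected ratio | SD 0.15 | SD 0.19 | SD 0.30 |
|---|---|---|---|---|
| Cohort 1 v Cohort 2 | 1.027–1.030 | about 11% | 10.5–10.8% | about 10% |
| Cohort 1 v Cohort 2 + Cohort 3 dose 5, n₃ = 6 | 1.61–1.64 | 82.3–84.0% | 71.9–74.5% | 51.6–53.8% |
| Same, n₃ = 8 | 1.69–1.73 | 95.7–96.7% | 88.4–90.2% | 66.3–69.0% |

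**Step 6, which reading the text supports.** Dose-normalised Cmax exists in Cohort 3 after doses 1 and 5, and SAP 4.6 takes only the first. That choice keeps accumulated exposure out of the test. Cmax needs the qualifier because a usable first-dose value exists in Cohort 3. AUCt has no first-dose value there, which leaves the two single-dose cohorts. The SAP 5 sentence is a convention for presenting data and does not define an analysis set.

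**Step 7, would AUC to infinity do better?** It removes the 3% truncation difference but extrapolates 4% to 8% of the area (1 - 0.956 = 0.044; 1 - 0.922 = 0.078). Suppose clearance were 20% lower at 800 mg, with the same volume and T = 31 days at 400 mg. The expected ratio is then 1.25 for AUC to infinity and 1.23 for AUCt, and 1 is excluded in 43% and 39% of trials. With 4 against 4 subjects the 90% limits lie a factor exp(1.943 × 0.19 × √(1/4 + 1/4)) = 1.30 either side of the estimate, so a 3% shift hardly matters.

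**The case for a change.** The strongest case for a change is that one phrase would close the gap, and that an open-label study should not leave an analysis set open until the data are in hand. Being optional does not excuse it: if the test is run, it returns a yes-or-no conclusion. The other grouping signals are also mixed, since the SAP sometimes says treatment dose where it could say treatment group. Nor does stretching the Cmax qualifier over both lines help. It would call for a first-dose AUCt in Cohort 3, which the SAP does not derive. Protocol 7.2 does list AUCt after each dose, but a 28-day first-dose value pooled with Cohort 2 would give a ratio of about 0.63 to 0.67, an error in the opposite direction.

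What stands is that the cohorts are not written down and that the wrong choice would mislead badly. What does not stand is that the plan leads there. The pooled reading would mix values differing about twofold at the same 800 mg dose. Individual parameters are listed under SAP 4.5, and accumulation after the fifth dose is itself a planned parameter, so the discrepancy would be hard to miss. First-dose Cmax is tested alongside. Dose escalation rests on safety review (Protocol 8.3 and 8.4.1), and nothing in the documents depends on this test.

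A further point concerns truncation. No quantification limit is given. If the last measurable sample were Day 90 at 400 mg and Day 120 at 800 mg, the Cohort 1 v Cohort 2 bias would be about 8% (ratio 1.077 / 1.083). That is still well inside the interval factor of 1.30. A cross-check is also already available, because the SAP derives "Total body clearance of drug from the serum (CL) after single dose (Cohort 1 and 2) and after dose 5 (Cohort 3"), and the reciprocal of single-dose clearance is dose-normalised AUC to infinity.

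**Conclusion.** The omission is real but needs no change. SAP 4.6 leaves the AUCt data set unstated. The sensible reading, Cohorts 1 and 2 after the single dose, is the one that its own treatment of Cmax implies. On that reading the bias is 2.7% to 3.0% and the test excludes 1 in 10% to 11% of trials against a nominal 10%.

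The large errors (expected ratio 1.61 to 1.73, wrong exclusion in 52% to 97% of trials over SD 0.15 to 0.30) belong to a pooling that no stated rule requires. Replacing AUCt by AUC to infinity would exchange a 3% bias for a modest extrapolation and leave the error rate essentially where it is.

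The sizes rest on mono-exponential decline, half-lives of 30.8 to 32.4 days, and an SD that the SAP labels within-subject. They are illustrative, but the contrast between the two readings does not depend on their exact values.

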8. INVESTIGATIONAL PLAN

8.1. Overall Study Design

This is a Phase 1, open-label, single ascending and multiple set dose study designed to evaluate the safety, tolerability, immunogenicity, PK, and PD of ALXN1210 in healthy Japanese subjects.

All subjects are to be screened for eligibility in the study after providing written informed consent to participate. Subjects who fail to meet eligibility criteria may not be rescreened for participation in the study, unless the condition that led to eligibility failure is transient, self-limited, and easily treatable, and is expected to be resolved at the time of dosing, as agreed by the investigator and medical monitor.

A total of 3 cohorts and up to 16 subjects are planned for evaluation. The cohorts will be enrolled sequentially and all subjects will receive IV ALXN1210:

[figure not shown]
- Cohort 1, 400 mg single dose (N = 4)
- Cohort 2, 800 mg single dose (N = 4)
- Cohort 3, 800 mg Q4W for a total of 5 doses (N = 6 to 8)

A Safety Review Committee (SRC) will conduct a review of the available clinical and safety data after the last subject in the 400 mg cohort (Cohort 1) has completed Day 15 to determine if dose escalation to 800 mg may proceed (Cohort 2). The SRC will conduct a review of all available clinical and safety data after the last subject in the 800 mg cohort (Cohort 2) has completed Day 15 to determine if dosing in Cohort 3 may begin. Dose escalation to the multiple repeated dose phase will proceed as scheduled and the study will continue as long as no prespecified toxicity events occur (see Table 3). Dose continuation within Cohort 3 after Period 2 will proceed following review of the available safety and tolerability data by the PI in accordance with the protocol's toxicity rules. Minimum data requirements do not apply for the PI review; however, it is expected to include available data up to 14 days after each dose.

Up to 2 subjects per cohort may be added if 2 or more subjects discontinue before Day 15 (first dose only for Cohort 3) for reasons other than drug-related AEs, and after consultation with the SRC. All enrolled subjects will be included in analyses as appropriate. Subjects who have been dosed and who withdraw from the study will be followed for safety assessments through the last study visit, if possible.

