19.7. Pharmacokinetic Analysis

The individual serum concentration data for ALXN1210-treated subjects, with actual sampling dates and times, will be used to derive the PK parameters by noncompartmental analyses using Phoenix WinNonlin 6.3 or higher.

The following PK parameters will be derived: maximum observed serum concentration (C_{max}) after each dose, time to maximum observed serum concentration (t_{max}), the observed minimum serum concentrations (C_{min}) just prior to Periods 2 to 5 (and 28 days after Period 5 dose) for Cohort 3, area under the serum concentration versus time curve from time 0 to the last quantifiable concentration (AUC_t) after each dose, area under the curve from time 0 (dosing) to the end of the dosing interval (AUC_t), apparent terminal-phase elimination rate constant (λ_z), terminal elimination half-life ($t_{1/2}$), total clearance (CL), volume of distribution (V_{ss}), assessment of steady-state, and accumulation at steady state. Assessment of dose proportionality and time linearity in PK parameters may be conducted.

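### SAP 4.6 declares dose proportionality whenever the 90% CI contains 1, so an imprecise result counts as proof

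*SAP*

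**What the plan says.** SAP section 4.6 makes the analysis optional: "Dose proportionality of the 400mg and 800mg ALXN1210 doses may be assessed for the following PK parameters". The parameters are dose-normalised AUCt and dose-normalised Cmax. For Cmax the section names Cohorts 1 and 2, and Cohort 3 after its first dose; for AUCt it names no cohorts. The method is the power model, "where the ratio of geometric means and the corresponding 90% confidence interval will be derived". The decision rule follows: "Dose proportionality will be concluded if the 90% confidence interval of the ratio contains 1".

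Protocol section 19.7 says only: "Assessment of dose proportionality and time linearity in PK parameters may be conducted". It gives no criterion, so SAP 4.6 is the sole rule. Neither document gives equivalence limits, a cap on interval width or an inconclusive category for this comparison. The sample-size text (Protocol 19.3, SAP 4.2) concerns the precision of AUC∞ and does not address dose proportionality.

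**The concern.** A 90% CI that contains 1 is the same event as not rejecting a ratio of 1 at two-sided 0.10. The rule fixes at 10% the chance of missing proportionality that is truly there. It puts no limit on the opposite error, declaring proportionality when it is absent. For any true ratio other than 1, the probability of concluding proportionality rises towards 90% as noise grows or groups shrink. A weak dataset is therefore more likely than a strong one to earn the favourable label.

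The groups are small: 4 subjects at 400 mg, against 4 at 800 mg for single-dose AUCt or 10 to 12 for first-dose Cmax. A departure is also plausible. Protocol section 5.1.1 reports that exposure in the earlier single-dose study rose slightly less than in proportion to dose between 200 mg and 400 mg. If the analysis is run as written, a real shortfall could be reported as dose proportional simply because the interval is wide.

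**Working it through.** The plan states no error rate or power for this rule, so there is no planned figure to reproduce.

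**Inputs**

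- Rule and confidence level: SAP 4.6.
- Group sizes: 4, 4 and 6 to 8 (Protocol 8.1, SAP 4.2). For Cmax this gives 4 v 10 (4 + 6) to 4 v 12 (4 + 8). For AUCt, 4 v 4 is inferred: SAP 2.2 and 4.5 derive AUCt after the single dose in Cohorts 1 and 2, but only after dose 5 in Cohort 3.
- Log-scale SD: an assumption. SAP 4.2 gives 0.19, "assuming the within-subject SD of the log-transformed" AUC∞. It is borrowed here as a between-subject SD for AUCt and Cmax, with a range of 0.10 to 0.30.
- True ratios of 0.90, 0.80 and 0.70: illustrative, because the documents give none.

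**Method**

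With two dose levels a factor of 2 apart, the power model reduces to a two-group comparison of log dose-normalised values: ratio = 2^(slope − 1). A numerical check gave the same ratio and CI both ways.

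- SE = SD × √(1/n1 + 1/n2)
- df = n1 + n2 − 2
- Noncentrality = ln(true ratio)/SE
- P(conclude) = P(−t < T < t), where T is noncentral t and t is the 95th percentile of central t

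For 4 v 4, SD 0.19 and true ratio 0.80: SE = 0.19 × √0.5 = 0.134, df = 6, t = 1.943, noncentrality = −0.223/0.134 = −1.66, and P = 0.568. Simulation gave 0.569.

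**Probability of concluding proportionality**

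| Comparison | True ratio | SD 0.10 | SD 0.19 | SD 0.30 |
|---|---|---|---|---|
| 4 v 4 | 0.90 | 63% | 82% | 87% |
| 4 v 4 | 0.80 | 13% | 57% | 76% |
| 4 v 4 | 0.70 | 0.3% | 24% | 56% |
| 4 v 10 | 0.80 | 3% | 41% | 67% |
| 4 v 12 | 0.80 | 2% | 39% | 66% |
| any | 1.00 | 90% | 90% | 90% |

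**Same estimate, different noise**

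Take an observed ratio of 0.80 with 4 v 4. The 90% CI is 0.80 ×/÷ exp(1.943 × SD × √0.5).

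- SD 0.10: 0.70 to 0.92, not proportional
- SD 0.19: 0.62 to 1.04, proportional
- SD 0.30: 0.53 to 1.21, proportional

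At SD 0.19, any observed ratio from 0.77 to 1.30 passes, since exp(±0.261) = 0.77 and 1.30.

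**Using the only between-subject variability in the documents**

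Protocol 8.3 gives half-life values that "ranged from 30.8 (10.2%) to 32.4 (16.2%) days over the studied doses", with the CV in brackets. Half-life is a different parameter, so this too is a proxy. SD = √ln(1 + CV²) gives 0.102 and 0.161. With 4 v 4 and a true ratio of 0.80, P(conclude) is then 14% and 46%.

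**The case against.** The logic and arithmetic are not in dispute; the case against is about importance and size.

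- **Low stakes.** Dose proportionality is not a study objective and is not among the listed PK endpoints. Escalation follows the Safety Review Committee and the toxicity rules. This stands, and it limits the consequence to one secondary PK statement. The optional wording, however, governs whether the analysis is run and not how it is judged once run.
- **The estimate is already planned.** SAP 4.6 derives the ratio and its CI, so a reader shown both would see a wide interval. This also stands. It makes the fix cheap, but it does not justify the label.
- **The size is not fixed by the documents.** The SD is borrowed and the true ratios are chosen. At a true ratio of 0.80 with 4 v 4, the answer runs from 13% to 76%. The 4 v 4 comparison is itself inferred, and Protocol 8.2 allows up to 6 subjects in each single-dose cohort; 6 v 6 at SD 0.19 gives 40% instead of 57%. These points stand as limits on the figures. The defect in the rule holds at any SD.
- **Noise does not always help.** At exact proportionality the probability is 90% whatever the noise. That is correct, but the error at issue arises when the ratio is not 1.
- **The opposite fault is mostly theoretical here.** The rule would also call a tight interval just off 1, such as 0.92 to 0.98, non-proportional. With these groups that needs an SD of about 0.02 to 0.03, well below any plausible value.

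**Conclusion.** The concern holds. As written, the rule turns absence of evidence against proportionality into a conclusion of proportionality, and nothing else in either document corrects it. With an assumed SD of 0.19, a true 20% shortfall in dose-normalised exposure would be declared proportional in 57% of trials for AUCt, and in 39% to 41% for first-dose Cmax. These sizes depend on the assumed SD and, for AUCt, on the inferred 4 v 4 comparison. The fault in the rule depends on neither. It should be fixed, but it does not affect the primary safety objective, dose escalation or any other trial decision.

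**What to change.** Delete the last sentence of SAP 4.6. Report the ratio of geometric means (or the power-model exponent) with its 90% CI as an estimate, and describe a wide interval that contains 1 as inconclusive. State which cohorts enter the AUCt comparison. If the sponsor wants a formal conclusion, allow it only when the whole 90% CI lies inside limits fixed before the data are seen.

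The cost is a small wording change, with no effect on design, sampling or data. The drawback is that a limit-based conclusion would often be out of reach. Taking 0.80 to 1.25 purely as an illustration, with SD 0.19 and exact proportionality, simulation with 400,000 draws gives a chance of meeting the limits of about 10% (4 v 4), 22% (4 v 10) and 25% (4 v 12). At that SD these cohorts can seldom support a positive claim, so reporting the estimate alone is the more practical choice.
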